8.2. Patient Discontinuation/Withdrawal from the Study

Patients may withdraw from the study at any time at his/her own request or may be withdrawn at any time at the discretion of the Investigator for safety, behavioral, compliance, or administrative reasons. This is expected to be uncommon.

If the patient withdraws consent for disclosure of future information, the Sponsor may retain and continue to use any data collected before such a withdrawal of consent.

Replacement patients may be enrolled in consultation with the Sponsor's Medical Monitor.

8.2.1. Investigational Product Discontinuation

If a patient is permanently discontinued from the IP, but agrees to study visits, the patient will come in for the Early Termination Visit and continue attending clinic visits as scheduled through the 24-week visit (from first dose). A final follow-up visit will not be required.

If a patient prematurely discontinues IP prior to the Week 24 Visit, the Investigator will make every attempt to perform a RHC, as clinically feasible, prior to or within 7 days of IP discontinuation (but after at least 12 weeks of IP), and prior to initiation of any new PAH medications.

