Study Week¹ (Days)	-4 Wks² (D-28 to D-1) Clinic	D1 Clinic	Wk 2 (D14) Telemed/ Phone Call	Wk 4 (D28) Clinic	Wk 8 (D56) Clinic or Home	Wk 12 (D84) Clinic	Wk 18 (D126) Clinic or Home	Wk 24 (D168) Clinic	Wk 28 (D196) FU ^{3/} ET ^{3,4} Clinic or Home
Vital Signs (BP, HR, RR, temp, oxygen saturation)	X	X		×	×	×	X	X	X
12-Lead ECG ¹²	X	X		×	×	×	×	X	×
Laboratory – Hematology, Coagulation ¹³ , Chemistry, urinalysis,	X	X		×	×	×	×	X	×
Columbia-Suicide Severity Rating Scale (C-SSRS)	X	X		×		×	×	X	X
Hospital Anxiety and Depression Scale (HADS)	X	X		×		×	×	X	X
Quick Inventory of Depressive Symptoms (QIDS-C)	X	X		×		×	×	X	X
Efficacy-Related Assessments									
5 TWM5	X	X		X		X		X	
Right Heart Catheterization (RHC) ¹⁴	X							X	X^{14}
Echocardiography ¹⁵	X					X		X	
WHO FC	X	X		X		X		X	
Plasma NT-proBNP level		×		×		×		×	
PAH Symptoms and Impact Questionnaire (PAH-SYMPACT)		X				×		X	
Actigraphy ¹⁶					\	$X \rightarrow$			
Pharmacokinetics									
Rodatristat PK Sampling ¹⁷		X		X		X		X	
Selexipag PK sampling ¹⁸		X		×					
Pharmacodynamics		Α		Þ		Þ		Α	
Ullile J-HIAA		< >		< >		< >		< >	
Plasma 5-HIAA ¹⁷		X		×		×		X	
Other									
Optional Blood for Future Research Sample		X						X	
Pharmacogenetic Samples		X						X	

Clinical Study Protocol Altavant Sciences GmbH

Visits at Week 2 (Telemed/Phone Call) and Week 4 (clinic visit) can occur within +/-2 days from the randomization date; Visits at Weeks 8 (Telemed/Phone call), 12 (clinic), 18 (clinic or home visit), 24 and 28/Follow Up (clinic) can occur within +/-5 days from the randomization date.

² Screening may be broken up into more than 1 visit, if necessary. Once all screening procedures are complete and the Investigator determines that the patient is eligible, the site must upload/send the required supporting documentation for approval by the Sponsor.

withdraw consent will continue to be followed for vital status from public records such as government vital statistics or obituaries, as allowed by local law, or periodic contact Patients who early terminate from the IP should be asked to return for visits as scheduled for ongoing assessments through the Week 28 Visit. Patients who withdraw consent should be asked to complete the Week 28 Visit for safety. Patients who have not completed the study as planned (through Week 24) cannot participate in OLE. Patients who (about every 6 to 12months).

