Patients that complete the study (defined as completing all visits through Week 24) have the option to enroll into the OLE (See Section 1.4). Patients who complete through Week 24 but decide not to enroll into the OLE, should complete the Week 28 Follow-Up Visit.

⁵ Weight only (no height or BMI) will be performed at Day 1 and Weeks 4, 8, 12, 24, and 28.

weight only (no height of Bivil) will be performed at Day 1 and weeks 4, 6, 12 6 Must have a confirmed diagnosis of PAH in patients' medical history

Background PAH therapy dose regimens must be stabilized for > 12 weeks prior to the screening RHC and on stable dose(s) > 8 weeks prior to the screening RHC to be eligible. All changes and dose adjustments in background PAH therapy must be documented.

Pregnancy tests not required for women who are surgically sterile. FSH required for women with amenorrhea < 2 years at the Screening Visit only to confirm postmenopausal

taken with food. During visits at the clinic or home, all assessments should be done predose, except where otherwise indicated. Patients should bring their IP with them for each IP must be taken daily, morning and evening until the night before the Week 24 visit. Patients must be told not to take a dose the morning of the Week 24 visit. Doses should be visit (including any empty bottles).

10 SAEs will be collected starting at informed consent form signing. AEs will be collected starting at first dosing.

every 4 weeks while on study. Weeks 8, 16 and 20 will be performed at home (with a kit given to the subject by the site) and the results will be confirmed with the subject by a procedures. If a positive result on a urine test, a serum pregnancy test should be completed to confirm. Pregnancy tests will be completed in women of child-bearing potential 11 Serum pregnancy tests will be performed at Screening and urine pregnancy tests over the rest of the study. A negative urine pregnancy test must be completed before Day 1 phone call. Additional pregnancy tests should be completed anytime menstruation is delayed and in women with infrequent or irregular menstrual cycles.

12 Three 12-lead ECGs (at least 1 minute apart) will be collected on Day 1 after at least 5 minutes of rest. Single 12-lead ECGs will be collected at all other time points.

¹³ Coagulation testing will be done at Screening, Weeks 12 and 24.

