4. STUDY DESIGN

4.1. Overall Design

This study will compare the efficacy, safety, and tolerability of 2 dosing regimens of rodatristat ethyl to placebo in patients with PAH over a 24-week treatment period. Investigational product (IP) will be administered on the background of stable PAH therapy.

Protocol RVT-1201-2002

Effective: 19JAN2022

Approximately ninety (90) patients will be enrolled. Patients will be randomized 1:1:1 to placebo, 300 mg BID, or 600 mg BID of rodatristat ethyl.

Eligible patients will be stratified based on the number of background PAH therapies they are receiving (1 vs 2 vs 3) and selexipag use (Yes/No). The number of patients who are on a prostanoid infusion will be capped at 50% of the total enrolled. The number of patients who are receiving selexipag will be capped at 20% of the total enrolled.

The study will consist of a Screening Period (up to 28 days in duration), a Baseline Period (Day 1), a 24-week Treatment Period (Main Study), and for patients that early terminate or do not enroll an Open-Label Extension (OLE), and a 4-week Follow-Up Period (approximately 4 weeks after the last dose), for a total study duration of 32 weeks.

Patients who complete the Main Study will have the option to enroll into an OLE and continue to receive rodatristat ethyl (those randomized to placebo will be re-randomized 1:1 to receive rodatristat ethyl 300 mg BID or 600 mg BID) for 6.5 years, until the Investigator or patient chooses to stop the IP, any stopping criteria in the Main Study are met, IP becomes commercially available, or the Sponsor stops the study for lack of efficacy or a safety signal (whichever preceding criteria comes first). In no case will a patient be allowed to exceed 10 years of exposure unless the product is approved for a chronic indication.

All participating patients will be required to be on a stable background therapy for PAH with mono, dual or triple combination therapy (which may include currently approved prostanoid therapies) at the time of Screening. All patients will maintain their standard of care (SOC) regimen at entry for the duration of the study. Refer to Section 6.6.2 for more details.

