9.3.1. Adverse Events of Special Interest

AESIs include:

- Severe constipation (and/or severe, persistent, or worsening abdominal pain)
- Depression/other significant mood-related disturbance (active suicidal ideation or behavior, severe depressive and/or anxious symptoms, other severe psychiatric TEAE)
- Elevations in hepatic enzymes (see Appendix 3)
- Diarrhea (see Appendix 2)

9.3.2. Time Period and Frequency for Collecting Adverse Event, Adverse Events of Special Interest, Serious Adverse Event Information

All SAEs will be collected from the signing of the ICF until the Follow-Up Visit at the time points specified in the SoA (Section 1.3). All AEs will be collected from the first dose of IP.

Medical occurrences that begin before the start of IP but after obtaining informed consent will be recorded on the Medical History/Current Medical Conditions section of the eCRF not the AE section.

All SAEs will be recorded and reported to the Sponsor or designee immediately and under no circumstance should this exceed 24 hours, as indicated in Appendix 14. The Investigator will submit any updated SAE data to the Sponsor within 24 hours of it being available.

Adverse events of special interest must be reported to the Sponsor should they meet the definition of an SAE, and all timelines for reporting of SAEs should be adhered to.

Investigators are not obligated to actively seek AEs or SAEs after conclusion of study participation. However, if the Investigator learns of any SAE, including a death, at any time after a patient has been discharged from the study, and he/she considers the event to be reasonably related to the IP or study participation, the Investigator must promptly notify the Sponsor.

9.3.3. Method of Detecting Adverse Events, Adverse Events of Special Interest, and Serious Adverse Events

The method of recording, evaluating, and assessing causality of AEs and SAEs and the procedures for completing and transmitting SAE reports are provided in Appendix 14.

Care will be taken not to introduce bias when detecting AEs and/or SAEs. Open-ended and non-leading verbal questioning of the patient is the preferred method to inquire about AE occurrences.

9.3.4. Follow-up of Adverse Events, Adverse Events of Special Interest, and Serious Adverse Events

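### Section 8.2.1 waives the follow-up visit for patients who stop IP early, while the schedule asks the same patients back through Week 28

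*Protocol*

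**What the plan says.** Protocol Section 8.2.1 applies to a patient who permanently stops IP but agrees to further visits. That patient has an Early Termination Visit, then keeps to the clinic schedule up to the 24-week visit. The section then says: "A final follow-up visit will not be required". The date of the last dose plays no part in this.

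Footnote 3 to the Main Study Schedule of Assessments (Section 1.3) says: "Patients who early terminate from the IP should be asked to return for visits as scheduled for ongoing assessments through the Week 28 Visit". Consent withdrawal has its own sentence: "Patients who withdraw consent should be asked to complete the Week 28 Visit for safety". So the first sentence of the footnote covers the patients of 8.2.1. Footnote 4 deals with completers: "Patients who complete through Week 24 but decide not to enroll into the OLE, should complete the Week 28 Follow-Up Visit".

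Section 4.1 gives patients who terminate early "a 4-week Follow-Up Period (approximately 4 weeks after the last dose"), and the synopsis lists a safety follow-up visit 4 weeks after dosing for anyone who does not enter the OLE. Section 7.4 offers the OLE only to patients who do not discontinue prematurely, so early stoppers fall in that group.

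On safety collection, Section 9.3.2 says: "All SAEs will be collected from the signing of the ICF until the Follow-Up Visit". The same sentence goes on to tie that visit to the timings in the Section 1.3 schedule, where it is Visit 9, Week 28, Day 196. For patients who leave without entering the OLE, SAP Section 8.2 counts events starting up to 28 days after the last dose as treatment-emergent. SAP Section 8.3.1 counts laboratory abnormalities up to the Week 28 follow-up or the first OLE dose.

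**The concern.** A site cannot carry out both instructions as written: one stops at Day 168 and the other at Day 196. With approximately 68 sites, similar patients could be observed for different lengths of time off drug, depending on which section the site reads.

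Two things follow where 8.2.1 is used. A patient who stops late has no scheduled contact during the last part of the SAP's 28-day window, so new events there depend on chance reporting. And the visit that closes SAE collection is one the patient is not required to make. Section 9.3.2 adds that "Investigators are not obligated to actively seek AEs or SAEs after conclusion of study participation", so the point at which participation ends matters.

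The waived visit has real content: vital signs, ECG, laboratory tests, the three mood and suicidality scales and, where applicable, a pregnancy test. Section 9.2.8 asks for close observation of mood and behavior around the end of treatment in particular.

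**Working it through.** No stated figure needs reproducing. The check sets the texts side by side and counts days.

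**Inputs.** Week 24 is Day 168 and Week 28 is Day 196 (Section 1.3). The visit window comes from footnote 1: "24 and 28/Follow Up (clinic) can occur within +/-5 days from the randomization date". The post-dose counting window is 28 days (SAP 8.2). Planned enrollment is 90 (Section 4.2). Half-lives are about 5 hours for rodatristat ethyl and 12 hours for rodatristat (Section 2.1). The rate of early stopping is not in the documents and is assumed below.

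**Who loses observation under 8.2.1.** A patient is observed for the full 28 days by Week 24 if the last dose is no later than 168 − 28 = Day 140. With the visit at the edges of its window, the cut-off is 163 − 28 = Day 135 or 173 − 28 = Day 145.

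**How much is lost.** Days off drug at each visit:

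| Last dose | Week 24 (Day 168) | Week 28 (Day 196) | Earliest Week 28 (Day 191) |
|---|---|---|---|
| Day 147 | 21 | 49 | 44 |
| Day 154 | 14 | 42 | 37 |
| Day 161 | 7 | 35 | 30 |

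For example, a last dose on Day 154 opens a window to Day 182, which is 182 − 168 = 14 days past the last visit that 8.2.1 requires. In all three cases footnote 3 covers the full 28 days, even at the earliest permitted Week 28 date.

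**Where the texts conflict.** Footnote 3 conflicts with 8.2.1 for every early stopper who stays in the study. Section 4.1 and the synopsis conflict with it only for late stoppers: with a last dose by about Day 140, a contact 4 weeks later already falls within the visits that 8.2.1 requires.

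**How many patients.** Assume that 5% to 20% stop IP early, evenly over 168 days.

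- Early stoppers: 90 × 0.05 = 4.5 to 90 × 0.20 = 18.
- Last dose in the final 28 days: 28/168 = 1/6, so 0.75 to 3 patients with fewer than 28 days observed.
- Last dose by Day 140: 140/168 = 5/6, so 3.75 to 15 patients with conflicting instructions but no shortfall in days.
- If half of the stoppers leave the study altogether under 8.2.2, for example because 8.1 requires withdrawal, the shortfall group is 0.375 to 1.5.

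The range for patients losing scheduled observation is therefore about 0.4 to 3.

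**Pharmacology.** Seven days off drug is 7 × 24 / 12 = 14 rodatristat half-lives.

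**The case against.** A reader might infer that the protocol sets no end to SAE collection for these patients. That goes too far. Read in full, the 9.3.2 sentence points to the schedule, and the schedule gives Week 28, Day 196. Section 9 also makes adherence to the schedule a requirement of study conduct. The endpoint is unclear only where a site lets 8.2.1 govern. The Early Termination Visit does not resolve this: under 8.2.1 it comes before the continued visits, so collection would end while the patient was still attending.

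A reader might also infer that a cooperative patient is followed less carefully than one who withdraws consent or skips the OLE. The documents do not support that either. Follow-up and early termination share one column (Visit 9). An 8.2.1 patient who attends the Early Termination Visit has had those procedures once, and the other two groups have not. Not requiring them a second time is a coherent choice.

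The wording can be partly reconciled: footnote 3 says patients should be asked, and 8.2.1 says the visit is not required, so a site could ask and accept a refusal. But 8.2.1 also ends scheduled attendance at Week 24, so the mismatch is milder, not gone.

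There are several safeguards. SAEs and AESIs already identified are followed to resolution or stabilization (9.3.4). Clinically significant laboratory abnormalities within 4 weeks of the last dose are repeated, and unscheduled assessments are allowed (9.2.5.5). Related SAEs learned of later must be reported (9.3.2). The drug clears quickly. All of this stands and limits the harm. None of it schedules contact to detect a new event in a late stopper, and none of it tells the site which instruction to follow.

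**Conclusion.** The contradiction is real and lies in current protocol text. Section 8.2.1 is the outlier against footnote 3, and for late stoppers also against Section 4.1 and the synopsis. Followed literally, it leaves patients with a last dose after about Day 140 short of 28 scheduled days off drug, and it makes the end of SAE collection ambiguous, though not absent.

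The effect is small. The estimate of about 0.4 to 3 patients rests on an assumed stopping rate, an even spread of stopping times and, at the lower end, an assumption that half leave the study. The SAP windows are counting rules and do not themselves require a visit. A reader might suspect an effect on the PVR analysis, but there is none: the primary endpoint is measured at Week 24 and both instructions keep these patients in the study to that visit. The correction is worth making because it concerns a safety-collection boundary and costs little.

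**What to change.** **Preferred.** In 8.2.1, delete the sentence waiving the final visit and state that visits continue through the Week 28/Follow-Up visit. This matches footnote 3 and gives 9.3.2 a visit that takes place. It is a one-sentence edit. The cost is one visit already in the schedule, at the clinic or at home, for each early stopper who stays: 4.5 to 18 under the assumption above if all of them stay. For those who stopped before about Day 140 it adds little safety information.

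**Alternative.** Keep a waiver only for patients at least 28 days past their last dose at Week 24. Write the same exception into footnote 3, and state in 9.3.2 that SAEs are collected until the later of the last study visit and 28 days after the last dose. This takes three matching edits but limits the extra visit to about 0.75 to 3 patients, or fewer if some leave the study.

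Neither option needs a change to the SAP.

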8.2.2. Study Discontinuation

If a patient who discontinues IP decides to end all study participation, an Early Termination Visit should be conducted, as shown in the SoA (Section 1.3), if possible.

Patients who withdraw should be asked if they may be contacted by the study site by telephone unless they explicitly withdraw their consent to be followed up.

If a patient withdraws consent, he/she may request destruction of any samples taken and not tested, and the investigator must document this in the site study records.

8.3. Lost to Follow up

A patient will be considered lost to follow up if he or she repeatedly fails to return for scheduled visits and is unable to be contacted by the study site.

The following actions must be taken if a patient fails to return to the clinic for a required study visit:

- The site must attempt to contact the patient and reschedule the missed visit as soon as possible and counsel the patient on the importance of maintaining the assigned visit schedule and ascertain whether or not the patient wishes to and/or should continue in the study.
- Before a patient is deemed lost to follow up, the Investigator or designee must make every effort to regain contact with the patient (where possible, 3 telephone calls and, if necessary, a certified letter to the patient's last known mailing address or local equivalent methods). These contact attempts should be documented in the patient's medical record.
- Should the patient continue to be unreachable, he/she will be considered to have withdrawn from the study.
- Patients who withdraw consent will continue to be followed for vital status from public records such as government vital statistics or obituaries, as allowed by local law, or periodic contact (about every 6 to 12 months).

Discontinuation of specific sites or of the study as a whole are handled as part of Appendix 5.

9. STUDY ASSESSMENTS AND PROCEDURES

Study procedures and their timing are summarized in the SoA in Section 1.3 for the Main Study and in Section 1.4 and Section 1.5 for the OLE.

Safety concerns should be discussed with the Sponsor immediately upon occurrence or awareness to determine if the patient should continue or discontinue IP.

Adherence to the study design requirements, including those specified in the SoA, is essential and required for study conduct.

All screening evaluations must be completed and reviewed to confirm that potential patients meet all eligibility criteria. The Investigator will maintain a screening log to record details of all patients screened and to confirm eligibility or record reasons for screening failure, as applicable.

Once all screening procedures are complete and the Investigator determines that the patient is eligible, the site must upload/send the required supporting documentation for approval by the Sponsor. The required information will include the RHC report (including tracings), PFTs obtained (may use PFTs completed in the 24 week period prior to screening or obtained at Screening), the screening echocardiogram, as well as specific information about the patient's medical history and disease state to further ensure the appropriateness of each patient being enrolled into this study. Approval from the Sponsor must be obtained prior to randomization.

All assessments should be completed predose unless otherwise stated.

If assessments are scheduled for the same nominal time, then the assessments should occur in the following order whenever possible: ECGs, vital signs, safety blood draws, PK blood draws.

Note: The timing of the assessments should allow the blood draw to occur as close as possible to the nominal time but before dosing.

Repeat or unscheduled samples may be taken for safety reasons or due to technical issues with the initial samples.

9.1. Efficacy Assessments

The efficacy-related assessments, as outlined below, will be obtained at time points indicated in the SoA in Section 1.3 and Section 1.4.

9.1.1. Right Heart Catheterization

The RHC is a common procedure used to diagnose PAH.

Cardiopulmonary hemodynamics will be assessed by RHC. All required RHC parameters must be collected using the same methods at Screening/Randomization and Week 24. The Screening/Randomization RHC will be required to confirm the diagnosis of PAH, and data from this RHC will serve as the baseline value for the primary and secondary analyses of cardiopulmonary hemodynamic parameters. Since the study is enrolling treatment-experienced patients, results from a historical RHC conducted prior to the Screening Visit are not expected to reflect the patient's current disease status unless it was performed within 4 weeks of the Screening visit, includes all required information, and provided that changes to the patient's PAH regimen were not made subsequent to that catheterization.

If prior approval is obtained from the Sponsor, the screening RHC may be performed on the same day as the randomization procedures, provided that all blood draws and efficacy assessments are conducted prior to the RHC procedure, and the RHC is performed prior to randomization and IP dosing. The hemodynamic assessment will be conducted in the supine position under resting conditions. The original RHC tracings will be maintained at the site. The

RHC tracings will have all personal health information removed and will be labeled with the

following: patient number, patient initials, protocol number, and date recorded.

Protocol RVT-1201-2002

Effective: 19JAN2022

Full details available in RHC manual.

